Previous studies have demonstrated the efficacy of ITA, at different concentrations ranging from 0.1 to 10 mg/mL at 0.1-0.2mL volumes.[6-8, 12] In these studies, nail psoriasis has been shown to significantly clinically improve with the treatment. The studies cited occurred mostly before the year 2000. In no studies to our knowledge were the concentrations compared directly. In 2000, the Nail Psoriasis Severity Index (NaPSI) was developed. The NaPSI is a nail psoriasis assessment tool developed by one of the leaders in the field of nail pathologies, [name]. This tool, detailed in Appendix A, allows researchers and clinicians to objectively quantify changes in psoriatic nails following treatments and study interventions.[13] Prior to 2000, authors used different methods to assess change following the study intervention, but most of these were qualitative. For example, Peachey et al. used a qualitative assessment (i.e. no improvement versus slight improvement versus marked improvement.) De Berker also used a qualitative assessment, but graded each feature of nail psoriasis (i.e. ridging, pitting, etc.) separately. The most recent study cited by Nantel-Battista et al., did use the NaPSI score. This score is increasingly widely used in studies of nail psoriasis.

The frequency and length of time that injections were administered in the cited studies varied between studies, but in most occurred at monthly intervals for 4-6 months. Four to six months is approximately the amount of time needed for the nail to completely grow, and therefore the amount of time necessary to see results from the study intervention.

Our approach is to investigate different concentrations of ITA in the treatment of nail psoriasis to determine which is the lowest effective concentration. All concentrations under investigation are part of standard clinical practice, as there is no consensus in the literature on the lowest effective concentration. Our study will consider only the fingernails, and not the toenails, of subjects with nail involvement for two reasons. First, toenail psoriasis is less common compared to fingernail psoriasis.[2] Second, in our clinical experience, patients are more motivated to treat fingernails, due to their important functions in daily activities, and for cosmetics. Thus, the treatment of fingernail psoriasis with ITA is most clinically relevant.

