Table 1: Randomization of subjects' fingernails to groups. Groups are numbered 1-5 and correspond to concentrations of ITA such that 1=2.5mg/mL; 2=5.0mg/mL; 3=7.5mg/mL; 4=10.0mg/mL; 5=placebo.

Procedures: Injections of ITA will be administered using standard methods. Hand hygiene procedures will be performed and the administrator will use gloves. Triamcinolone acetonide, at the determined dose, will be drawn into a solution of 1% lidocaine. The nail fold of the affected nail will be cleaned with an alcohol swab. In addition to the local anesthetic given as part of the injection, the area will be anesthetized with an ethyl chloride spray immediately prior to injection using a 30 gauge needle. During injection, the participant may experience light pressure. Following injection, the wound will be covered with a bandage. A board-certified dermatologist will perform all procedures and will be present to monitor for unlikely adverse events, such as excessive bleeding.

None of these procedures differ from the current standard of care. The only aspect that will differ in the treatment of affected nails is the concentration of ITA used. However, there is no current standard of care regarding the concentration; all concentrations under investigation are part of typical clinical practice and have been validated in studies.[1] The purpose of this study is to determine the lowest effective concentration of ITA in the treatment of nail psoriasis.

The schedule of treatments is as follows:

Treatment will be performed using ITA with a frequency of once per 6 weeks +/- 1 week. A follow-up visit will be performed at 24 weeks, ending the study period.

The following will be performed at the first visit:

- Completion of Nail Psoriasis Severity Index
- Collection of survey to document subject's quality of life
- Use the study intervention (intralesional triamcinolone acetonide injections) on the subject's fingernail(s)
- Take pictures of subject's nails before and possibly after treatment
- Take an X-ray of the affected hand

The following procedures will be performed at every treatment visit after the first, and at the follow-up visit:

- Measurements of clear nail growth (in millimeters), clear nail area (in mm²)
- Completion of Nail Psoriasis Severity Index.
- Use the study intervention (intralesional triamcinolone acetonide injections) on the subject's fingernail(s)
- Take pictures of subject's nails before and possibly after treatment

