Skin atrophy	0 = none 1 2 3 = extreme
Bleeding	0 = none 1 2 3 = extreme
Burning/cold sensation	0 = none 1 2 3 = extreme
Hematoma	0 = none 1 2 3 = extreme

Other (please describe and grade, or enter '0' for none)	
--	--

Table 1. The physician shall evaluate the patient's response to the treatment and screen for possible side effects as listed. 0 = none, 1 = mild, 2 = moderate and 3 = extreme.

Photos shall be taken of any visible treatment effects.

EFFICACY EVALUATIONS

The primary endpoint of this study is to assess the lowest effective concentration of intralesional triamcinolone acetonide in the treatment of nail psoriasis. Safety and tolerability shall be determined based on the reported number of adverse events as outlined in the Adverse Events Section and subject-reported symptoms (if any).

In order to evaluate the efficacy of the proposed treatment, high quality photographs will be taken before and after treatment using standardized lighting, exposure settings, and subject positioning. Trained individuals shall assess the changes in the photographs as outlined in the following paragraphs.

Preliminary assessment of the efficacy of the study intervention will be determined by measuring the amount of clear nail growth. This growth will be compared to the initial amount of clear nail recorded at baseline. Changes in clear area and NaPSI will also be reviewed as study intervention progresses and compared to baseline values.

INSTITUTIONAL REVIEW BOARD

Prior to beginning this study, approval for all study related documents (protocol, consent form, advertising) will be obtained from the Weill Cornell Medical College IRB.

DATA ANALYSIS

Efficacy will be evaluated using nail plate measurements to assess clear nail plate growth and rates of clinical improvement. Clinical improvement will be assessed using the NaPSI, an objective validated measuring tool developed by one of the leaders in the field of nail pathology for use in clinical trials on treatment of nail psoriasis.

Adverse effect intensity will be assessed at each of the treatment visits using a 0-3 scale (0=none, 1=mild, 2=moderate, 3=severe) for each side effect with changes from baseline analyzed using the Wilcoxon signed-ranks test and presented as medians and ranges.

Statistical analysis will be performed using SAS version 9.2 (SAS Institute, Cary, NC). Two-tailed $P < 0.05$ will be considered statistically significant.

MONITORING AND QUALITY ASSURANCE

Site Monitoring

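### Clear nail growth and clear nail area are to be compared with baseline, but no visit list schedules either measurement before the first injection

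*Combined protocol and SAP*

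**What the plan says.** Efficacy Evaluations gives clear nail a definite role: "Preliminary assessment of the efficacy of the study intervention will be determined by measuring the amount of clear nail growth". It then fixes the comparator: "This growth will be compared to the initial amount of clear nail recorded at baseline". Clear area and NaPSI are treated alike: "Changes in clear area and NaPSI will also be reviewed as study intervention progresses and compared to baseline values". Data Analysis again names clear nail as an efficacy measure: "Efficacy will be evaluated using nail plate measurements to assess clear nail plate growth and rates of clinical improvement".

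The visit lists are in Research Design / Methods. Clear nail growth in mm and clear nail area in mm² appear in the list introduced by "The following procedures will be performed at every treatment visit after the first, and at the follow-up visit", and again in the list for the follow-up visit only. They are absent from the screening list and from the first-visit list. The first-visit list does include NaPSI, the quality-of-life survey, the injection, photographs and an X-ray.

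On photographs, Efficacy Evaluations says that "high quality photographs will be taken before and after treatment using standardized lighting, exposure settings, and subject positioning", and adds: "Trained individuals shall assess the changes in the photographs as outlined in the following paragraphs".

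**The concern.** The analysis text relies on a starting value that no visit is assigned to collect. Staff who work from the lists would score NaPSI at the first visit and have no prompt to measure clear nail. A pre-treatment measurement that is missed cannot be taken once the nail has been injected.

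The primary objective is to compare concentrations. Nails enter with differing amounts of clear plate, and the comparison with baseline is what removes that difference. If the 50 rows of Table 1 are filled, each of the five groups has 50 / 5 = 10 nails, so chance imbalance in starting clear nail is a practical possibility. Without a starting value it could be neither described nor adjusted for on this measure.

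Two other conflicts in the same lists bear on what is done to the nail and when. The list shared by later treatment visits and follow-up includes an injection, so read literally it places one at the visit that closes the study; the follow-up-only list has none. The screening list also contains an injection, which does not fit the two-month washout and re-evaluation required of subjects already using nail treatments.

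**Working it through.** The plan gives no figure to reproduce. The check sets the lists against the baseline comparisons.

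| List (Research Design / Methods) | NaPSI | Clear nail growth and area | Photographs | Injection | Adverse events |
|---|---|---|---|---|---|
| Screening visit | no | no | yes, after consent (text following the list) | yes | no |
| Re-evaluation after washout | no | no | no | no | no |
| First visit | yes | no | yes, before treatment | yes | no |
| Treatment visits after the first, and follow-up | yes | yes | yes | yes | yes |
| Follow-up visit only | yes | yes | yes | no | no |

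1. **Scheduled values before the first injection.** Clear nail growth: 0. Clear nail area: 0. NaPSI: 1, at the first visit, provided it is scored before the injection there and no injection was given at an earlier screening visit. Two of the three measures in Efficacy Evaluations therefore lack a scheduled baseline.

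2. **Timing of the first listed clear-nail value.** Treatments are 6 ± 1 weeks apart, so the second treatment visit falls 6 − 1 = 5 to 6 + 1 = 7 weeks after the first injection.

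3. **Visit count (inferred, not stated).** The protocol gives the interval and a follow-up at week 24, but not the number of treatments. With a six-week interval, 24 / 6 = 4 intervals, which gives visits at weeks 0, 6, 12, 18 and 24. If screening and first visit are one visit, clear nail is listed at 4 of these 5 visits and NaPSI at 5 of 5.

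4. **Photographs as a substitute.** Lighting, exposure and positioning are standardized. Nothing is said about a scale in the image, calibration, or how a length or an area is read from it. In the shared list the measurements and the photographs are separate items, so the text does not settle whether the later mm and mm² values come from the nail or from the image.

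5. **Injection at week 24.** The shared list names the follow-up visit and includes the injection; the follow-up-only list omits it. Both describe the same visit and they disagree.

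6. **Injection at screening.** The quality-of-life survey, the X-ray and the injection are on both the screening and first-visit lists, which suggests that the two may be one visit. The protocol does not say so. If they are separate, an injection at screening would also precede the first scheduled NaPSI.

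**The case against.** The strongest reply is that the protocol clearly intends a baseline. It speaks of an initial amount recorded at baseline, schedules photographs before the first injection, and places the clear-nail paragraph directly after the sentence on assessing photographs. On that reading photographs are the planned method throughout and the baseline exists in them. Much of this stands. The intent is plain, and the photographs could partly supply the value. What remains is that no list assigns the measurement to a visit before injection, and no scale or method is given for turning an image into mm or mm².

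It is also fair to say that clear nail growth is called a preliminary assessment, while NaPSI is the measure named in the efficacy objective and is on the first-visit list. That limits the consequence but does not supply the clear-nail comparison the plan promises.

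A reader might go further and infer that the value at about week 6 would serve as the reference and hide early differences between concentrations. The documents do not support this. No section uses week 6 as a reference, and the words initial and baseline exclude it. The Introduction/Background also says that "Four to six months is approximately the amount of time needed for the nail to completely grow", and links that period to when results are seen, so a large early difference cannot be presumed.

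A reader might also infer that adverse events go uncollected at week 24, because the follow-up-only list omits them. That is not so: the shared list expressly covers the follow-up visit, and Adverse Events and Reporting makes the assessment ongoing.

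**Conclusion.** The inconsistency is real and can be checked directly. Two of the three efficacy measures in Efficacy Evaluations are to be compared with baseline but have no scheduled value before the first injection; the first listed value comes five to seven weeks after it. This rests on reading the lists as complete, which is how visit staff would use them. The documents do not show that the baseline would in fact be missing, since photographs may partly fill the gap, and they give no basis for computing a bias. No sample size or error rate is affected.

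The injection items at week 24 and at screening are genuine drafting conflicts of lesser weight. The first would, if followed, give a steroid injection with no later scheduled visit. The second matters for the NaPSI baseline only if screening and first visit are separate. The whole point should be fixed because the correction is nearly free and a missed pre-injection measurement cannot be recovered.

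**What to change.** - Add clear nail growth (mm) and clear nail area (mm²) to the first-visit list. State that these, NaPSI and the photographs are all completed before the injection.
- State how the two clear-nail measurements are made and use the same method at every visit. If they are read from photographs, specify the scale and the reading procedure.
- In the list shared by later treatment visits and follow-up, limit the injection item to treatment visits, so that none is given at week 24. Leave adverse-event collection as it is; it already applies there.
- Remove the injection from the screening list, or state that screening and first visit are the same visit, held after washout where washout applies.

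The cost is a few minutes of measurement at a visit already planned, with edits to the visit lists and the case report form.

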- Collection of adverse events, if there are any

The following procedures will be performed at the follow-up visit only:

- Measurements of clear nail growth (in millimeters), clear nail area (in mm²)
- Completion of Nail Psoriasis Severity Index.
- Take pictures of subject's nails
- Collection of survey to document subject's changes in quality of life since the beginning of the study intervention and subjective assessment of nail since the beginning of the study intervention

ADVERSE EVENTS AND REPORTING

Adverse event/effect (AE) assessment will be ongoing throughout the study. All adverse events shall be reported by the clinical Investigator to the Sponsor and IRB following WCMC's reporting policies.

Unanticipated Adverse Effect (UAE)

An unanticipated adverse effect is an adverse effect on health and safety caused by, or associated with, the study intervention, if that problem was not previously identified in nature, severity, or degree of incidence in the investigational plan or application, or any other unanticipated problem that relates to the rights, safety, or welfare of subjects.

The Investigator shall be responsible for determination of the causal relationship of all adverse events to the study intervention and/or procedure. The Principal Investigator is responsible for monitoring the safety of the subjects enrolled.

Any adverse events will be reviewed and analyzed by the Principal Investigator as soon as the event occurs and will be documented in the subject's binder. Any unexpected adverse reactions will be reported by telephone to the IRB within 48 hours of observing the event.

No major adverse effects are anticipated during this study; however, we will screen for severe pain (Pain \geq 8/10 on self-reported scale).

The following minor adverse effects are anticipated: cold/burning sensation, minor to moderate pain (Pain \leq 7 on VAS scale), minor swelling (edema), minor hematomas, and temporary erythema (redness). We will screen for additional possible but not expected adverse effects. If the minute treatment reaches an intolerable threshold of pain $>$ 7, the study intervention will be stopped and more anesthetic may be applied if appropriate. Such pain could result from local injection of the skin. A physician will be on site for the to assess for adverse events as needed.

POTENTIAL ADVERSE EFFECTS:	
Epidermal/Nail Response Assessed	Grading
Pain	0 = none 1 2 3 = extreme
Persistent Erythema	0 = none 1 2 3 = extreme

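### Read literally, the plan gives an injection at the week-24 visit that ends the study; read without that injection, it schedules no 0–3 side-effect grade after the last treatment visit

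*Combined protocol and SAP*

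**What the plan says.** Under RESEARCH DESIGN / METHODS, Procedures, the schedule is "Treatment will be performed using ITA with a frequency of once per 6 weeks +/- 1 week", followed by "A follow-up visit will be performed at 24 weeks, ending the study period". Two lists then cover that last visit.

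- The shared list is headed "The following procedures will be performed at every treatment visit after the first, and at the follow-up visit". Its items are the clear-nail measurements, NaPSI, the injection, photographs before and possibly after treatment, and "Collection of adverse events, if there are any".
- The follow-up list is headed "The following procedures will be performed at the follow-up visit only". It repeats the clear-nail measurements, NaPSI and photographs (with no mention of treatment) and adds the survey. It contains no injection and no adverse-event item.

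EARLY TERMINATION gives a subject who stops early a final visit with the same procedures as the follow-up visit.

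On safety, ADVERSE EVENTS AND REPORTING says "Adverse event/effect (AE) assessment will be ongoing throughout the study". Its grading table includes skin atrophy and persistent erythema, and the caption names no visit. DATA ANALYSIS does name the visits for the grade: "Adverse effect intensity will be assessed at each of the treatment visits using a 0-3 scale". Changes from baseline in that grade are to be tested with the Wilcoxon signed-rank test.

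**The concern.** A site that follows the shared list's heading as written would inject at week 24, after which nothing is observed. It would also inject a subject at the visit where that subject leaves the trial. Neither the benefit nor the delayed harm of that injection could be recorded at a later visit.

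A site that omits the injection meets a different problem. The 0–3 grade is tied to treatment visits, so its last scheduled value falls on the day of the last injection. Skin atrophy and persistent erythema from that injection would need time to appear. The background section itself lists thinning of the skin at the injection site among the steroid's side effects. Side effects by concentration are a secondary objective, and the hypothesis concerns the balance of efficacy and safety. The graded scale is also the only safety outcome for which the plan names a test. A planned grade after the full course would therefore be useful, and the subject is already in the clinic at week 24.

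**Working it through.** No sample-size or power figure bears on this point. The check compares the lists and works through the visit schedule.

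**Step 1: what each reading provides at week 24.**

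| Reading | Injection | Scheduled adverse-event collection | Scheduled 0–3 grade |
|---|---|---|---|
| Shared list in full | Yes | Yes | Only if week 24 counts as a treatment visit; no visit follows that day's injection |
| Follow-up list alone | No | No | No |
| Non-treatment items of the shared list, plus the follow-up list | No | Yes | No |

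Both readings without an injection leave the grade unscheduled, because the DATA ANALYSIS sentence names treatment visits only. Whether adverse-event collection is scheduled depends on which of those two readings is taken.

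**Step 2: length of the ungraded interval if week 24 has no injection.** Inputs from Procedures are an interval of 6 weeks ± 1 week and follow-up at week 24. Assumptions: the first injection is at week 0, which the plan does not state, and spacing is constant.

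- 6-week spacing (nominal): injections at weeks 0, 6, 12, 18; interval 24 − 18 = 6 weeks.
- 5-week spacing: weeks 0, 5, 10, 15, 20; interval 24 − 20 = 4 weeks.
- 7-week spacing: weeks 0, 7, 14, 21; interval 24 − 21 = 3 weeks.

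**Step 3: size of the extra injection if the shared list is followed in full.** On the nominal schedule there are five injections (weeks 0, 6, 12, 18, 24) instead of four. The volume is 0.1–0.2 mL and the concentration 2.5–10 mg/mL, so one injection delivers between 0.1 × 2.5 = 0.25 mg and 0.2 × 10 = 2.0 mg per nail treated with triamcinolone. At the highest concentration and volume, the cumulative dose per nail is 5 × 2.0 = 10 mg instead of 4 × 2.0 = 8 mg.

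**Step 4: which reading is likelier.** The schedule separates treatment visits from the follow-up visit, and the follow-up list drops both the injection and the reference to treatment in its photograph item. These point to no injection at week 24. The spacing does not settle it, because week 24 fits the nominal 6-week interval exactly.

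**The case against.** The strongest reply is that the lists can be read together sensibly. The shared list's heading expressly covers the follow-up visit, so its non-treatment items apply there, and the follow-up list adds the survey. Adverse events are then collected at week 24 and nobody is injected. Four further points support that side:

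- EFFICACY EVALUATIONS bases safety and tolerability on the number of reported adverse events and on subject-reported symptoms, and event assessment is continuous. That serves the objective on the rate and nature of side effects without any grade.
- The nails are examined, scored and photographed at week 24 in any case, so visible atrophy or erythema could be noticed and reported.
- The plan does not say whether grading precedes or follows the day's injection. Pain, bleeding, burning or cold sensation, and hematoma could be graded at the last treatment visit itself.
- Delayed effects of earlier injections can be graded at later treatment visits.

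All of this stands and it narrows the point. A reader might infer that no safety information is gathered after the last injection; the documents do not support that. A reader might also infer that the plan must produce either an unobserved injection or a missing adverse-event collection. The combined reading avoids both. It does not supply a scheduled 0–3 grade at week 24, and it depends on the site setting aside part of a list whose heading applies to the visit without exception.

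**Conclusion.** The point holds in a limited form and is of low severity. As written, the shared list's heading places an injection at the visit that ends the study and, through EARLY TERMINATION, at a leaver's closing visit. The follow-up list suggests that this is unintended. If week 24 has no injection, delayed effects of the last injection have no scheduled 0–3 grade. The ungraded period is the final 6 weeks on the nominal schedule, or 4 or 3 weeks at constant 5- or 7-week spacing, assuming a first injection at week 0.

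The consequence is confined to the graded side-effect analysis, whose last planned value is taken at the last treatment visit. Event reporting continues. Nothing here shows that the final efficacy score would change, so a reader should not extend the point to efficacy. Nor can the amount of information lost be stated by nail or by concentration, because the plan does not say that grading is done by nail; the table caption speaks of the patient's response.

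**What to change.** 1. Procedures, shared list: strike the last clause of the heading, so that the list covers only treatment visits after the first.
2. Procedures, follow-up list: add adverse-event collection and the 0–3 grading. This must accompany step 1, which on its own would remove the only text placing adverse-event collection at week 24.
3. DATA ANALYSIS: extend the sentence on the 0–3 scale to include the follow-up or closing visit as well as treatment visits.
4. EARLY TERMINATION: state that no injection is given at the closing visit.
5. Record the grade by treated nail, so that it can be compared by concentration.

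The cost is a few wording changes and one short side-effect grading at a visit that already takes place.

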Washout Period: Subjects who are using any form of treatment on their nails at the time of the screening visit may participate in the study provided that they are willing to undergo a two-month washout period. During this time, they must abstain from using any nail treatments (including, but not limited to: spa nail treatments, nail polish use, prescribed topical or systemic medications indicated for the nails, over the counter nail treatments, or any other nail intervention with the exception of routine clipping and washing.) After the washout period, the subject may be re-evaluated for participation in the study.

Enrollment and Randomization: Patients with at least two affected fingernails will be enrolled. For each participant, one fingernail will receive an intralesional injection of 0.1-0.2 mL of normal saline (placebo). The other affected fingernail(s) will receive an injection of 0.1-0.2mL of a pre-determined concentration of ITA. Four concentrations of ITA will correspond to four study groups: 2.5mg/mL, 5mg/mL, 7.5mg/mL and 10mg/mL. Participants' fingernails will be randomized such that there are approximately equal numbers of fingernails in each of the five groups (four study interventions, one placebo). To avoid bias, fingernails will be assigned to groups systematically. Fingernails will be assigned to groups in order of anatomical convention. For example, if the subject has involvement of both the thumb, forefinger and third finger of the right hand, the thumb is the first digit, so, if involved, it will be assigned first according to the table below. If a subject has involvement of fingernails of both the right and left hand, the fingernails of the right hand will be assigned before the left. The table assumes that up to 50 nails will be affected between the 10 subjects enrolled. In our clinical experience, this is a reasonable expectation. If more or fewer fingernails are involved during the enrollment period, the randomization table will be adjusted accordingly. The concentration of ITA injected will be different for each group. All other study procedures will be the same between groups.

Fingernail	Group
1	5
2	3
3	4
4	1
5	2
6	4
7	5
8	1
9	3
10	2
11	3
12	4
13	5
14	1
15	2

16	2
17	1
18	3
19	5
20	4
21	5
22	4
23	3
24	2
25	1
26	1
27	2
28	3
29	4
30	5
31	1
32	2
33	4
34	3
35	5
36	5
37	3
38	4
39	2
40	1
41	1
42	3
43	4
44	2
45	5
46	1
47	5
48	2
49	4
50	3

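### Clear nail is recorded in absolute mm and mm² while nails enter a list not balanced by digit, so nail size can distort the clear-area comparison between concentrations in either direction

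*Combined protocol and SAP*

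**What the plan says.** - **Measurements.** The Procedures section lists "Measurements of clear nail growth (in millimeters), clear nail area (in mm²" for each treatment visit after the first and for the follow-up visit. The first-visit list has NaPSI and photographs but no clear-nail measurement.
- **Use.** Efficacy Evaluations says of clear nail growth: "This growth will be compared to the initial amount of clear nail recorded at baseline". It adds: "Changes in clear area and NaPSI will also be reviewed as study intervention progresses and compared to baseline values". Data Analysis says: "Efficacy will be evaluated using nail plate measurements to assess clear nail plate growth and rates of clinical improvement". No efficacy model, covariate or test is named, and nothing divides by plate size.
- **Allocation.** Under Enrollment and Randomization, "Fingernails will be assigned to groups in order of anatomical convention", the right hand before the left; "the thumb is the first digit, so, if involved, it will be assigned first according to the table below". The aim is that "there are approximately equal numbers of fingernails in each of the five groups". Balance by digit is not mentioned.
- **Planned size.** "The table assumes that up to 50 nails will be affected between the 10 subjects enrolled".

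**The concern.** Digits have plates of different size. If two nails clear by the same proportion, the larger one gains more mm². Taking the difference from the nail's own baseline does not remove this. With plate area A and clear fractions p0 at baseline and p1 later, the gain is A × (p1 − p0), which still carries A. A group that happens to hold more thumbs would then show more clear area with no better response.

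The primary objective is to find the lowest effective concentration, with about ten nails per group. A spurious gap in clear area could make one concentration look better or worse than its neighbour.

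**Working it through.** **Inputs from the plan.** The 50-row list and group codes (1 = 2.5, 2 = 5, 3 = 7.5, 4 = 10 mg/mL, 5 = placebo); ten participants; thumb-first order.

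**Assumed, not in the documents.** Thumb plate area r times the other nails, r = 1.5, 2 or 2.5, with the other four nails equal; equal proportional clearing in all groups.

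**1. The plan's own figure.** 10 participants × 5 nails = 50 rows. The list has 10 rows per group, and each consecutive block of five rows holds every group once. The approximate equality by group is reproduced.

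**2. Thumbs when every participant has five nails on one hand.** Thumbs take rows 1, 6, 11, …, 46, which carry groups 5, 4, 3, 2, 5, 1, 1, 5, 1, 1. The tally for groups 1 to 5 is 4, 1, 1, 1, 3.

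**3. Mean plate area, other nails = 1.**
- 2.5 mg/mL: (6 + 4r)/10
- 5, 7.5 and 10 mg/mL: (9 + r)/10 each
- placebo: (7 + 3r)/10

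| r | 2.5 mg/mL | each higher concentration | placebo | excess over higher | excess over placebo |
|---|---|---|---|---|---|
| 1.5 | 1.20 | 1.05 | 1.15 | 14% | 4% |
| 2 | 1.40 | 1.10 | 1.30 | 27% | 8% |
| 2.5 | 1.60 | 1.15 | 1.45 | 39% | 10% |

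With equal proportional clearing, mean clear area differs by the same percentages.

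**4. One participant changed.** Let the first participant have two nails, thumb included, and the other nine five nails on one hand. Reading the list literally, thumbs take rows 1, 3, 8, 13, 18, 23, 28, 33, 38, 43, which carry groups 5, 4, 1, 5, 3, 3, 3, 4, 4, 4. The tally is 1, 0, 3, 4, 2. Only 47 rows are used, so 10 mg/mL has 9 nails and 2.5 mg/mL has 10. Mean areas are (5 + 4r)/9 and (9 + r)/10. For r = 1.5, 2, 2.5 these are 1.222 against 1.05, 1.444 against 1.10 and 1.667 against 1.15. Now 10 mg/mL exceeds 2.5 mg/mL by 16%, 31% or 45%.

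**5. Mixed involvement.** A simulation of 10,000 runs drew 2 to 8 involved nails per participant at random, with assumed plate sizes 1.6, 1.1, 1.15, 1.05 and 0.7 from thumb to little finger. The ratio of mean nail size, 2.5 mg/mL to each other group, averaged 0.99 to 1.01, with a 95% range of about 0.78 to 1.28. Thumb counts differed by three or more between the highest and lowest group in 61% of runs.

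**6. Effect on a test, before and after scaling.** This used the allocation of step 2 with no true difference, r = 1.25 to 2.0, fraction cleared with mean 0.4 and SD 0.1 to 0.3, and a two-sided t-test at 0.05 (10,000 runs per setting). The test, mean and SD are assumptions. In mm², 2.5 mg/mL was falsely favoured over another active concentration in 3.4% to 9.3% of runs, against a nominal 2.5%. For 2.5 against 5 mg/mL the range was 3.6% to 9.3% in mm² and 2.3% to 2.7% as a fraction of plate.

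**The case against.** **Direction.** A reader might infer from step 2 that the list is biased toward 2.5 mg/mL and so toward the study hypothesis. The documents do not support that. The figure of 50 nails is an upper planning figure, and no text says that each participant has five nails on one hand. Step 4 reverses the direction by changing one participant, and step 5 shows no average tilt. The hypothesis also concerns the ratio of efficacy to safety, not the largest clear area. Four or more of ten thumbs in one given group has probability about 12% under independent assignment at 1 in 5, so the tally is not evidence of a faulty list. This objection stands.

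**Adjustable list.** The plan says that the table will be adjusted if nail numbers differ, and it requires one placebo nail per participant. The literal reading in step 4 breaks that rule for some participants (rows 8 to 12 contain no placebo). The actual tally cannot be predicted, but neither provision balances digits.

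**Absolute analysis is inferred.** The units are recording units, and a comparison with baseline could mean a ratio. A ratio, A·p1/(A·p0), would cancel plate size. That is fair. But the plan does not say so, and a ratio is undefined or unstable for a nail with little or no clear plate at baseline.

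**Importance.** Clear nail growth is called a preliminary assessment. NaPSI, the measure named for the placebo objective and for clinical improvement, is scored by quadrant (0 to 8 per nail) and does not depend on plate size. This limits the damage to the clear-nail measures. For growth in mm there is no figure, because the documents do not say how linear growth varies by digit.

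**Conclusion.** The concern holds as a risk of avoidable distortion with no fixed direction. Clear area in mm² is not scaled to the plate, and allocation is not balanced by digit, so nail size can differ between concentration groups. With five nails on one hand per participant, the spurious excess for 2.5 mg/mL is 14% to 39% over each higher concentration and 4% to 10% over placebo. With one participant changed, 10 mg/mL leads 2.5 mg/mL by 16% to 45%. The thumb counts follow from the printed list and the stated involvement patterns. The percentages rest on assumed plate-size ratios and on equal proportional clearing. The error rates rest in addition on an assumed test and variance. The conclusion applies to clear area, is unquantified for growth in mm, and does not touch NaPSI. It merits a change because the remedy is simple and can be set before data are seen.

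**What to change.** 1. Add the clear-nail measurement to the first-visit list. Efficacy Evaluations needs a baseline value that the list does not collect.
2. At every visit, measure total plate area (and length) together with the clear portion, from the photographs already planned.
3. In Data Analysis, make the clear-nail efficacy variable the percent of that nail's plate that is clear, compared between groups with adjustment for the same nail's baseline percent. Report mm and mm² descriptively.
4. Optionally add a thumb indicator, which costs one degree of freedom and addresses thumb differences other than size.

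The cost is one more measurement per nail per visit and a sentence or two of analysis text. The list and the NaPSI assessment need not change for this point.
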